4.5 Study Drug Description

The Sponsor or designee will provide the Research Pharmacists at the sites with vials containing study drug (active ibalizumab) manufactured under current Good Manufacturing Practices (cGMP). Ibalizumab is provided as a parenteral formulation in a 2 mL, clear-glass vial. The drug product contains ibalizumab at a concentration of 150 mg/mL, histidine United States Pharmacopoeia (USP), sucrose, sodium chloride, polysorbate 80, and water for injection USP at pH 6.0. Each vial contains either at least 1.2 mL of fluid delivering a total of 180 mg study drug per vial (Lot 201403001) or at least 1.33 mL of fluid delivering a total of 200 mg study drug per vial (Lots 201509019 and 201505012). Labeling will clearly identify the configuration of vials in each carton and of each individual vial.

4.6 Study Drug Packaging, Storage, and Disposal

Study drug is provided as a single-use parenteral formulation in a 2 mL, clear-glass vial containing either at least 1.2 mL (Lot 204103001) or at least 1.33 mL (Lots 201509019 and 201505012) of drug product. The stability of the ibalizumab drug product at 2°C to 8°C is evaluated in ongoing studies. Study drug will be shipped under refrigerated conditions with a temperature-monitoring device.

Ibalizumab vials should be stored refrigerated at 2°C to 8°C (but NOT FROZEN) and protected from light. Investigator sites must store the investigational product in a secure location and maintain a temperature log of the storage conditions.

The temperature must be continuously monitored with a continuous-monitoring temperature device. Temperature logs must be available for review at each site-monitoring visit. Temperature excursions outside the required limits should be reported promptly to the Sponsor, and the affected study drug should not be administered to any study patients until further instruction. The Sponsor or designee will investigate temperature excursions and adjudicate the disposition of any affected study drug.

Any spent vials or remaining contents of used vials should be destroyed according to the site's procedures for spent vial destruction and disposal, but only after complete drug accountability records have been reviewed and accepted during routine monitoring and after written permission has been given for spent vial destruction. The destruction should be recorded.

4.7 Study Drug Accountability

The investigator will maintain accurate records of receipt of the entire supply of the study drug, including when, how much of, and conditions under which the study drug is received, dispensed, and destroyed by site personnel. In addition, the administration of study drug to each patient should be documented to the vial level for each infusion (i.e., lot number of every vial for that infusion, time of infusion bag preparation, time of administration, and documentation of full infusion received). Reasons for departure from the expected dispensing regimen must also be recorded. Drug accountability will be reviewed and documented at each study visit. Reconciliation and accountability of study drug will be done throughout the study during the monitoring visits. After the completion of the study, the Sponsor or designee may authorize the site to dispose of unused supplies of the investigational drug, provided this alternative disposition does not expose humans to risks from the drug. The Sponsor or designee shall maintain written records of all drug dispositions, which will include the name of the investigator; the date, quantity, batch, or code of each such shipment; and method of disposal.

5. Patient Enrollment

It is anticipated that approximately 50 patients will be enrolled at approximately 50 sites in North America and Taiwan; however, the numbers of participating patients and sites will not be limited and may exceed 50. Patients will be enrolled only if they meet all of the inclusion criteria and none of the exclusion criteria.

5.1 Inclusion Criteria

Patients may be enrolled in Cohort 1 if they meet both of the following criteria:

1. Are currently receiving ibalizumab via other TaiMed-sponsored or Investigator-sponsored IND protocol
2. Are capable of understanding and have voluntarily signed the informed consent document

Patients may be enrolled in Cohort 2 if they meet all of the following criteria:

1. Are 18 years of age or older
2. Are capable of understanding and have voluntarily signed the informed consent document
3. Have documented HIV-1 infection by official, signed, written history (e.g., laboratory report); otherwise, an HIV-antibody test will be performed
4. Are able and willing to comply with all protocol requirements and procedures
5. Have a viral load >1,000 copies/mL and documented resistance to at least one antiretroviral medication from each of three classes of antiretroviral medications as measured by previous resistance testing (resistance testing is not provided by the study for qualification purposes)
6. Have a history of at least 6 months on antiretroviral treatment
7. Are receiving a failing antiretroviral regimen OR have failed and are off therapy
8. Have viral sensitivity/susceptibility to at least one antiretroviral agent other than ibalizumab, as determined by previous resistance test performed within 6 months prior to Screening and be willing and able to be treated with at least one agent to which the

patient's viral isolate is fully sensitive/susceptible according to the Screening resistance tests as a component of the OBR

9. If sexually active, are willing to use an effective method of contraception during the study and for 30 days after the last administration of the study drug

5.2 Exclusion Criteria

There are no Exclusion Criteria for patients meeting the Inclusion Criteria for Cohort 1.

For Cohort 2, patients having or meeting any of the following conditions or characteristics will be excluded from the study:

1. Eligible for participation in other TaiMed Biologics-sponsored clinical trials of ibalizumab
2. Any significant diseases (other than HIV-1 infection) or clinically significant findings, including psychiatric and behavioral problems, determined from Screening, medical history, and/or physical examination that, in the investigator's opinion, would preclude the patient from participating in this study
3. Any significant acute illness within 1 week before the first administration of investigational medication on this study
4. Any active infection secondary to HIV requiring acute therapy; however, patients who require maintenance therapy (i.e., secondary prophylaxis for opportunistic infections) will be eligible for the study
5. Any immunomodulating therapy (including interferon), systemic steroids, or systemic chemotherapy within 4 weeks before Day 0
6. Any prior exposure to ibalizumab (formerly TNX-355 and Hu5A8)
7. Any vaccination within 7 days before Day 0
8. Any female patient who is pregnant, intends to become pregnant, or is currently breastfeeding
9. Any current alcohol or illicit drug use that, in the investigator's opinion, will interfere with the patient's ability to comply with the study schedule and protocol evaluations
10. Any previous clinically significant allergy or hypersensitivity to any excipient in the ibalizumab formulation

11. Any radiation therapy during the 28 days before first administration of investigational medication on this study
12. Any clinically significant Grade 3 or 4 laboratory abnormality according to the DAIDS grading scale, except for the following asymptomatic Grade 3 events:
 - triglyceride elevation
 - total cholesterol elevation

5.3 Patient Withdrawal and Discontinuation

5.3.1 Reasons for Withdrawal

A patient may be withdrawn from the study if the patient:

- Withdraws consent to participate or requests an early discontinuation at any time during the study
- Is in violation of the protocol
- Becomes pregnant during the study (see [Section 8.7](#) for a description of procedures to be followed in case of pregnancy)
- Experiences virologic failure
- Experiences a treatment-related serious or intolerable AE(s) (according to DAIDS criteria, see Appendix B)
- Experiences toxicity, defined as two consecutive laboratory results, at least 14 days apart, with a CD4⁺ cell count below 200 cells/mm³ that also represents a 50% reduction from the baseline CD4⁺ cell count

The study treatment should be discontinued for all Grade 3 or 4 treatment-related abnormalities, as defined in Appendix B. Treatment-emergent Grade 3 or Grade 4 lab abnormalities should be retested within 72 hours. Any patient with a Grade 3 or Grade 4 lab abnormality that resolves before the next scheduled dose may have the study drug reinstated. If a patient develops a persistent Grade 3 or Grade 4 treatment-emergent laboratory abnormality, excluding triglycerides and cholesterol, that does not resolve prior to the next scheduled study drug administration, study drug may be discontinued.

A patient experiencing one or more treatment-emergent SAEs will receive treatment and follow-up evaluations by the Principal Investigator, or they will be referred to another appropriate physician for treatment and follow-up. Withdrawal from the study will be at the discretion of the Principal Investigator/Sponsor.

The investigator will also withdraw a patient if the Sponsor or local regulatory agency (e.g., FDA) terminates the study. Upon occurrence of an SAE, the Principal Investigator will notify the Sponsor or designee of these events via the SAE hotline. If a patient is discontinued because of an AE, the

event will be followed until satisfactory resolution or until the Principal Investigator deems the event to be chronic or the patient to be stable.

5.3.2 Handling Withdrawals and Discontinuations

Patients are free to withdraw from the study at any time upon request. Patient participation in the trial may be stopped at any time at the discretion of the investigator or at the request of the Sponsor or designee. At the time of withdrawal or discontinuation, the investigator will assess the best options for treatment and discuss these options with the patient.

When a patient withdraws or is discontinued from the study, the reason(s) for withdrawal or discontinuation will be recorded by the investigator. Whenever possible, all patients who withdraw, or are discontinued from the study prematurely, will undergo all Early Withdrawal procedures as described in the Schedule of Events in Section 3.4. Patients who fail to return for final assessments will be contacted by the site personnel in an attempt to have the patients comply with the protocol. A minimum of two documented phone calls should be made over the course of at least 2 weeks. If the site personnel receive no response, they should send a certified letter requesting that the patient contact the site regarding their status in the study. If the patient does not respond at this point, the date the certified letter was mailed will be considered the date of study withdrawal.

In the event of a patient death during the study, the date of death (as listed on the death certificate) will be used for the date of study discontinuation.

It is vital to obtain follow-up data on any patient withdrawn because of an AE or SAE. In such cases, the patient will be followed to satisfactory resolution or until the Principal Investigator deems the event to be chronic or the patient to be stable. In any case, every effort must be made to undertake protocol-specified safety follow-up procedures.

5.3.3 Sponsor or Regulatory Agency Termination of Study

Although the Sponsor intends to complete the study, the right is reserved to discontinue the study at any time for clinical or administrative reasons, upon commercial availability of ibalizumab, or if

required by the local regulatory authority (e.g., FDA). If the Sponsor discontinues the study, the FDA will be notified promptly.

6. Study Visits

6.1 Cohort 1: 800 mg Every 2 Weeks

Since there are no laboratory parameters required for entry into Cohort 1 of this study, Screening procedures and Day 0 procedures are scheduled for the same day. Patients who qualify for entry into Cohort 1 of this study who are currently receiving 800 mg ibalizumab every 2 weeks will have physical and laboratory measures performed and receive the first on-study dose of ibalizumab at Screening/Day 0 as specified in the Schedule of Events (see Table 3-1). These patients will return to the clinic on Day 14 and every 2 weeks thereafter through the remainder of participation in the study for study drug administration (800 mg) and effectiveness and safety evaluations. Patients who are discontinued or who withdraw from the study prematurely will be asked to return for an Early Withdrawal visit to have all assessments detailed in the Schedule of Events for that visit performed.

6.1.1 Screening/Day 0

Screening and Day 0 (first on-study administration of ibalizumab) are scheduled for the same day. At this visit, study information will be reviewed and discussed, and the informed consent form will be reviewed and signed by the participant. No procedures, other than a preliminary verbal assessment of eligibility by review of inclusion/exclusion criteria, may be done before the informed consent process is complete. Once informed consent has been obtained and documented, the following procedures may be completed (pre-infusion):

- Record demographics, medical history (general and HIV), and the patient's height
- Record all prior ART exposure; record all other medications taken within the last 30 days
- Record results of a complete physical examination
- Record vital sign measurements

- Record the patient's weight
- Record all AEs that begin after the patient has signed the informed consent (see [Section 8.1](#) for definitions)
- Collect blood and urine for the following laboratory samples:
 - Hepatitis serology and C-reactive protein
 - Clinical laboratory assessments (serum chemistry, hematology, and urinalysis; see [Section 7.2.2](#) for a complete list of parameters)
 - Archive sample
 - Serum pregnancy test in females of childbearing potential and a follicle-stimulating hormone (FSH) test in postmenopausal females
 - HIV-1 RNA (viral load)
 - HIV-1 viral resistance sample (will be stored for later use if needed)
 - CD4⁺ cell count (within 1 hour before the start of the infusion)
 - Immunogenicity of ibalizumab

After the preceding procedures are completed, site personnel will undertake the following (infusion and post-infusion):

- Administer study medication (800 mg)
- Record vital sign measurements after the completion of the infusion and observe the patient for at least 15 minutes
- Record AEs

6.1.2 Events for Day 14 (± 1 day) and Weeks 4, 6, 8, 10, 14, 16, 18, 20, 22, 26, 28, 30, 32, 34, 38, 40, 42, 44, 46, 50, 52, 54, 56, 58, 62, 64, 66, 68, 70, 74, 76, 78, 80, 82, 84, 86, 88, 90, 92, 94, 98, 100, 102, 104, 106, 110, 112, 114, 116, 118, 122, 124, 126, 128, 130, 134, 136, 138, 140, and 142 (± 2 days)

The following will be completed before study drug administration:

- Record vital sign measurements
- Record AEs and concomitant medications
- Assess adherence to the OBR (Weeks 4, 8, and 84 only)
- Collect urine sample for the following:
Urine pregnancy test for females of childbearing potential (Weeks 4, 8, 16, 20, 28, 32, 40, 44, 52, 56, 64, 68, 76, 80, 84, 88, 92, 100, 104, 112, 116, 124, 128, 136, and 140 only)

Site personnel will undertake the following after administration of study drug (800 mg):

- Record vital sign measurements after completion of infusion and observe patient for at least 15 minutes
- Record AEs

6.1.3 Events for Weeks 12, 24, 36, 48, 60, 72, 96, 108, 120, 132, 144/EOS and 150/Follow-up (± 2 days)

The following will be completed before study drug administration:

- Record results of physical examination (complete exam at Weeks 24, 48, 72, 96, 120, 144, and 150; abbreviated exam at Weeks 12, 36, and 60)
- Record the patient's weight (Weeks 12, 24, 36, 48, 60, 72, 96, 120, 144 and 150 only)
- Record vital sign measurements

- Record AEs and concomitant medications
- Assess adherence to the OBR
- Collect blood and/or urine samples for the following:
 - Hepatitis serology and C-reactive protein (Weeks 24, 48, 96, and 150 only)
 - Clinical laboratory assessments (serum chemistry, hematology, and urinalysis; See [Section 7.2.2](#) for a complete list of parameters) (Weeks 12, 24, 36, 48, 60, 72, 96, 120, and 150 only)
 - Archive sample (Weeks 12, 24, 36, 48, 60, 72, 96, 120, 144, and 150 only)
 - Pregnancy test for females of childbearing potential (urine at Weeks 12, 36, 60, 108, 120, 132, 144, and 150 only); serum at Weeks 24, 48, 72, and 96 only)
 - HIV-1 RNA (viral load)
 - HIV-1 viral resistance sample (will be stored for later use if needed)
 - CD4⁺ cell count (within 1 hour before the start of the infusion)
 - Immunogenicity of ibalizumab (Weeks 24, 48, 72, 96, 120, 144, and 150 only).

Site personnel will undertake the following after administration of study drug (800 mg) (not done at Week 150/Follow-up):

- Record vital sign measurements after completion of infusion and observe patient for at least 15 minutes
- Record AEs

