3.4 Schedule of Events

The Schedule of Events is presented in Tables 3-1 and 3-2 for Cohort 1 patients receiving ibalizumab 800 mg every 2 weeks, in Tables 3-3 and 3-4 for Cohort 1 patients receiving ibalizumab 2,000 mg every 4 weeks, and in Tables 3-5 and 3-6 for patients in Cohort 2. Throughout the study, patients are not required to fast before collection of blood samples for safety or effectiveness. However, patients should adhere to dietary recommendations as suggested for the components of their OBR or other concomitant medications.

Table 3-1. Schedule of Events: Cohort 1 – 800 mg every 2 weeks, Screening through Week 4

	Study Visit		
	Screening/ Day 0	Day 14	Week 4
Visit window (days)	N/A	±1	±2
ACTIVITIES TO BE COMPLETED BEFORE STUDY DRUG ADMINISTRATION			
Discuss the inclusion/exclusion criteria	X		
Obtain a signed informed consent form	X		
Record demographics, medical history (general and HIV), height	X		
Record all prior ART exposure; record all other medications within the last 30 days	X		
Assess adherence to the OBR			X
Record results of a complete physical examination	X		
Record vital sign measurements	X	X	X
Record the patient's weight	X		
Record AEs	X ⁴	X	X
Record concomitant medications		X	X
BLOOD ¹ AND/OR URINE SAMPLES TO BE COLLECTED BEFORE STUDY DRUG ADMINISTRATION			
Hepatitis serology, C-reactive protein	X		
Hematology, serum chemistry, urinalysis (see Section 7.2.2)	X		
Archive sample	X		
Serum for pregnancy test for females of childbearing potential ²	X		
Urine for pregnancy test for females of childbearing potential			X
HIV-1 RNA (viral load)	X		
HIV-1 viral resistance sample ³	X		
CD4 ⁺ T-cell count ⁵	X		
Immunogenicity of ibalizumab (2 tubes x 3 mL each) ⁵	X		
STUDY DRUG ADMINISTRATION AND AFTER			
Administer study medication	X	X	X
Record vital sign measurements and observe (15 min.) after infusion	X	X	X
Record AEs	X	X	X

- ¹ Patients need not fast before blood sampling.
- ² Serum FSH test to be conducted on postmenopausal females at Screening only.
- ³ Viral resistance testing will include assessments of reverse transcriptase, protease, integrase, and envelope (entry) genes and chemokine coreceptor utilization; the samples will be collected and stored, and testing will only be performed for patients who experience virologic failure while on the study.
- ⁴ Only record AEs that are related to study procedures before administration of the first dose.

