Table 3-3. Schedule of Events: Cohort 1 – 2,000 mg every 4 weeks, Screening through Week 8

	Study Visit		
	Screening/ Day 0	Week 4	Week 8
Visit window (days)	N/A	±2	±2
ACTIVITIES TO BE COMPLETED BEFORE STUDY DRUG ADMINISTRATION			
Discuss the inclusion/exclusion criteria	X		
Obtain a signed informed consent form	X		
Record demographics, medical history (general and HIV), height	X		
Record all prior ART exposure; record all other medications within the last 30 days	X		
Assess adherence to the OBR		X	X
Record results of a complete physical examination	X		
Record vital sign measurements	X	X	X
Record the patient's weight	X		
Record AEs	X	X	X
Record concomitant medications		X	X
BLOOD ¹ AND/OR URINE SAMPLES TO BE COLLECTED BEFORE STUDY DRUG ADMINISTRATION			
Hepatitis serology, C-reactive protein	X		
Hematology, serum chemistry, urinalysis (see Section 7.2.2)	X		
Archive sample	X		
Serum for pregnancy test for females of childbearing potential ²	X		
Urine for pregnancy test for females of childbearing potential		X	X
HIV-1 RNA (viral load)	X		
HIV-1 viral resistance sample ³	X		
CD4 ⁺ T ⁺ -cell count ⁴	X		
Immunogenicity of ibalizumab (2 tubes x 3 mL each) ⁴	X		
STUDY DRUG ADMINISTRATION AND AFTER			
Administer study medication	X	X	X
Record vital sign measurements and observe (15 min.) after infusion	X	X	X
Record AEs	X	X	X

- ¹ Patients need not fast before blood sampling.
- ² Serum FSH test to be conducted on postmenopausal females at Screening only.
- ³ Viral resistance testing will include assessments of reverse transcriptase, protease, integrase, and envelope (entry) genes and chemokine coreceptor utilization; the samples will be collected and stored, and testing will only be performed for patients who experience virologic failure while on the study.
- ⁴ Samples to be drawn within 1 hour before the start of the infusion (if infusion is scheduled for that visit).

Abbreviations: AE = adverse event; ART = antiretroviral therapy; CD4⁺ = helper T-cell; FSH = follicle-stimulating hormone; HIV = human immunodeficiency virus; OBR = optimized background regimen

Table 3-4. Schedule of Events: Cohort 1 – 2,000 mg every 4 weeks, Week 12 through end of study

Week	Study Visit											
	12	16	20	24	28	32	36	40	44	48	52	56
Visit window (days)	±2	±2	±2	±2	±2	±2	±2	±2	±2	±2	±2	±2
ACTIVITIES TO BE COMPLETED BEFORE STUDY DRUG ADMINISTRATION												
Record results of a complete physical examination				X						X		

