6.2 Cohort 1: 2,000 mg Every 4 Weeks

Since there are no laboratory parameters required for entry into Cohort 1 of this study, Screening procedures and Day 0 procedures are scheduled for the same day. Patients who qualify for entry into Cohort 1 of this study who are currently receiving 2,000 mg ibalizumab every 4 weeks will have physical and laboratory measures performed and will receive the first on-study dose of ibalizumab at Screening/Day 0, as specified in the Schedule of Events (see Table 3-3). These patients will return to the clinic at Week 4 and every 4 weeks thereafter through the remainder of participation in the study

for study drug administration (2,000 mg) and effectiveness and safety evaluations. Patients who are discontinued or who withdraw from the study prematurely will be asked to return for an Early Withdrawal visit to have all assessments detailed in the Schedule of Events for that visit performed.

6.2.1 Screening/Day 0

Screening and Day 0 (first on-study administration of ibalizumab) are scheduled for the same day. At this visit, study information will be reviewed and discussed, and the participant will review and sign the informed consent form. No procedures, other than a preliminary verbal assessment of eligibility by review of inclusion/exclusion criteria, may be done before the informed consent process is complete. Once informed consent has been obtained and documented, the following procedures may be completed (pre-infusion):

- Record demographics, medical history (general and HIV), and the patient's height
- Record all prior ART exposure; record all other medications taken within the last 30 days
- Record results of a complete physical examination
- Record vital sign measurements
- Record the patient's weight
- Record AEs that begin after the patient signs the informed consent (see [Section 8.1](#) for definitions)
- Collect blood and urine for the following laboratory samples:
 - Hepatitis serology and C-reactive protein
 - Clinical laboratory assessments (serum chemistry, hematology, and urinalysis; see [Section 7.2.2](#) for a complete list of parameters)
 - Archive sample
 - Serum pregnancy test in females of childbearing potential and an FSH test in postmenopausal females
 - HIV-1 RNA (viral load)
 - HIV-1 viral resistance sample (will be stored for later use if needed)

- CD4⁺ cell count (within 1 hour before the start of the infusion)
- Immunogenicity of ibalizumab

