6.4 Early Withdrawal Procedures

Patients who withdraw from the study at any time before Week 96/EOS will be asked to complete all Early Withdrawal procedures to ensure safety and collect as much effectiveness data as possible.

The following procedures will be completed at the Early Withdrawal visit (study drug is not administered at Early Withdrawal):

- Record results of a complete physical examination
- Record the patient's weight
- Record vital sign measurements

- Record AEs and concomitant medications
- Assess adherence to the OBR
- Collect blood and/or urine samples for the following:
 - Hepatitis serology and C-reactive protein
 - Clinical laboratory assessments (serum chemistry, hematology, and urinalysis; see [Section 7.2.2](#) for a complete list of parameters)
 - Archive sample
 - Serum pregnancy test for females of childbearing potential
 - HIV-1 RNA (viral load)
 - HIV-1 viral resistance sample (will be stored for later use if needed)
 - CD4⁺ cell count
 - Immunogenicity of ibalizumab

6.5 **Unscheduled Visits**

Unscheduled visits are allowed for the following reasons:

- To perform a confirmatory plasma viral load determination
- To perform confirmatory laboratory testing for clinically abnormal values
- Any time the investigator feels that they are clinically required for safety reasons related to the patient's participation in this trial

Findings during these unscheduled visits must be reported in the EDC system under the unscheduled visit section.

7. Study Assessments

A central laboratory will analyze all blood and urine samples with the exception of the HIV-1 resistance testing and immunogenicity testing, which will be undertaken by appropriate specialty contract laboratories. Urine samples will be analyzed at the site; if abnormal results are obtained for a patient, a urine sample will be sent to the central laboratory for microscopic evaluation.

The following assessments will be conducted at the times indicated in the Schedule of Events (Tables 3-1 through 3-6).

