If a patient or investigator suspects that the patient may be pregnant before study drug administration, the study drug must be withheld until the results of laboratory pregnancy testing are available. If pregnancy is confirmed, the patient must not receive the study drug and must be withdrawn from the study. The investigator must immediately notify the medical monitor of a pregnancy associated with study drug exposure and record the event on the Pregnancy Surveillance Form that will be provided to each site. Protocol-required procedures for study discontinuation must be performed on the patient unless contraindicated by pregnancy (e.g., x-ray studies). Other appropriate follow-up procedures should be considered if indicated.

The investigator must follow up with a pregnant patient or the pregnant partner of any sexually active male patient every 4 weeks while the woman is pregnant and every 4 weeks thereafter to follow perinatal and neonatal outcome. The investigator must report follow-up information regarding the course of the pregnancy, including perinatal and neonatal outcome, on the appropriate Pregnancy Surveillance Form. Infants who result from such pregnancies should be followed for a minimum of 8 weeks for safety assurances.

Pregnancy Surveillance Forms will be submitted to the Westat Regulatory Affairs Department via the SAE fax line. HHS encourages the reporting of all in utero exposures to antiretroviral agents to the Antiretroviral Pregnancy Registry ([contact] or [contact]).

9. Statistical Considerations

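### Cohort 1 Screening/Day 0 schedules only a serum pregnancy test, drawn at the dosing visit, and unless pregnancy is suspected or confirmed no text requires the result before the infusion

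*Protocol*

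**What the plan says.** For Cohort 1, Protocol 6.1 states that "Screening procedures and Day 0 procedures are scheduled for the same day", and 6.2 has the same arrangement for the 2,000 mg regimen. Both sections explain that entry depends on no laboratory parameter. Section 5.2 sets no exclusion criteria for Cohort 1, so pregnancy is not a listed bar to entry.

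The pregnancy test at that visit is serum in both regimens:

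- 800 mg (6.1.1): "Serum pregnancy test in females of childbearing potential and a follicle-stimulating hormone (FSH) test in postmenopausal females".
- 2,000 mg (6.2.1): "Serum pregnancy test in females of childbearing potential and an FSH test in postmenopausal females".
- Tables 3-1 and 3-3 mark the row "Serum for pregnancy test for females of childbearing potential" at Screening/Day 0 and leave the urine row blank until Week 4.

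The block of the tables that holds these rows is headed in terms of "URINE SAMPLES TO BE COLLECTED BEFORE STUDY DRUG ADMINISTRATION". The text then moves to dosing: "After the preceding procedures are completed, site personnel will undertake the following (infusion and post-infusion").

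The opening of Section 7 gives the general rule on analysis: "A central laboratory will analyze all blood and urine samples with the exception of the HIV-1 resistance testing and immunogenicity testing". Serum pregnancy tests are not among the exceptions.

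Section 8.7 contains the only rules that link a pregnancy result to dosing. One covers suspicion and makes dosing wait for the laboratory: "If a patient or investigator suspects that the patient may be pregnant before study drug administration, the study drug must be withheld until the results". The other bars drug and requires withdrawal once pregnancy is confirmed.

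**The concern.** Section 7.2.5 says pregnancy tests are done to protect the fetus because the risk is unknown, and 8.7 says a woman with a confirmed pregnancy must not be dosed. A routine test earns its place by finding a pregnancy that nobody suspects. At Cohort 1 entry the sample is drawn and the drug is given at one visit, and nothing written makes the second step wait for the result of the first. A result that arrives after the visit can report a dose given in an unsuspected pregnancy but cannot prevent it.

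What is at stake is the safety of a small, uncounted group of women at one visit. The estimates and the analysis are not affected.

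**Working it through.** The plan states no figure on this point, so the check is mainly a side-by-side reading.

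**1. What is scheduled around the Day 0 infusion**

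| Item | Cohort 1, 800 mg | Cohort 1, 2,000 mg | Cohort 2 |
|---|---|---|---|
| Serum test | Day 0, the dosing visit (Table 3-1) | Day 0, the dosing visit (Table 3-3) | Screening, Weeks -6 to -1 (Table 3-5) |
| Urine tests before the Day 0 infusion | 0 | 0 | 1 (6.3.2) |
| Pregnancy listed as an entry exclusion (5.2) | No | No | Yes |
| Written rule that the Day 0 test must be negative before the infusion | None | None | None |
| Next scheduled pregnancy test | Urine, Week 4 | Urine, Week 4 | Urine, Week 4 |

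**2. Does completing the preceding procedures amount to a result rule?** The procedure listed before the infusion in 6.1.1 and 6.2.1 is collection of samples, and the table heading also speaks of collection. A site that draws the serum and then infuses has followed the text.

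**3. Does another section supply the rule?**

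- 7.2.5 requires withdrawal of a patient who becomes pregnant but does not tie dosing to a result.
- 8.7 ties dosing to a result only when pregnancy is suspected or confirmed.
- 5.2 and the opening of 6.1 and 6.2 give no entry condition that would do it.

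For an unsuspected pregnancy at Cohort 1 Day 0, no such rule remains.

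**4. Size**

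- Scheduled infusions from Day 0 to Week 144: 144/2 + 1 = 73 at 800 mg every 2 weeks, and 144/4 + 1 = 37 at 2,000 mg every 4 weeks. The Day 0 dose is 1 of 73 or 1 of 37. These counts locate the dose in the schedule; they do not measure risk.
- On-study doses given before the Day 0 result: 0 if the result is back before the infusion, at least 1 if it is not. Turnaround is not stated, so a late result is an assumption, and no upper end is claimed.
- The next scheduled test is 4 × 7 = 28 days later (window ±2 days).
- The number of women of childbearing potential in Cohort 1 is not given.

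**The case against.** The strongest case on the other side has five parts.

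*The harm is assumed.* It needs a serum result that comes back after the infusion. The laboratory manual is not in the documents, and 11.8 allows for local laboratories. This stands, and it is why the range starts at 0. The gap in the text remains, because sites that follow the protocol may act differently.

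*Other safeguards exist.* Section 8.7 requires contraception, tells women to report a suspected pregnancy at once, and withholds drug on suspicion. Cohort 1 patients are already on ibalizumab (5.1) and may have been tested under their earlier protocols, which cannot be seen here. This also stands and limits the benefit.

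*Testing is periodic by design.* On the 800 mg schedule a pregnancy test falls at Day 0 and every 4 weeks, which is 144/4 + 1 = 37 visits. That leaves 73 - 37 = 36 infusions with no test. The protocol therefore accepts roughly four-weekly surveillance. That is a fair reason not to ask for a test at every infusion. It is a weaker answer at Day 0, where the protocol already schedules a test and only the timing of the result is open.

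*Cohort 2 has no written result rule for its Day 0 test either.* Correct. A reader might infer that Cohort 2 has a formal gate that Cohort 1 lacks; the text does not support that. The difference is in the schedule: Cohort 2 has serum at Screening and urine before the Day 0 infusion. Nor should a reader infer that the protocol is silent on where urine is read. Section 7 says urine is analyzed at the site, although its next clause suggests that urinalysis was meant, so the wording is ambiguous.

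*The change may reach few women.* A footnote to one of the SAP laboratory listings says laboratory samples were not collected at TMB-311 Screening for Cohort 1, and SAP 3.4.1 already counts two patients from investigator INDs. This suggests, without proving, that some Cohort 1 entry is past. The footnote also conflicts with Tables 3-1 and 3-3. It does not show that a result was in hand before dosing.

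**Conclusion.** The point holds as a cheap safety improvement. At Cohort 1 Screening/Day 0, in both regimens, a site can follow the plan exactly and give one further dose in an unsuspected pregnancy before the serum result is known. Whether that happens rests on an unstated turnaround: 0 doses if the result is back in time, at least 1 if not.

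Three stronger readings are tempting and are not supported:

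- That the plan lets a woman with a known or suspected pregnancy be dosed. Section 8.7 forbids it.
- That Day 0 is a first fetal exposure to the drug. Cohort 1 patients enter already on treatment.
- That a stated share of all tested visits lacks protection or would be covered by a fix. Such a share depends on the test type at Week 144/EOS, where 7.2.5 says serum and Tables 3-2, 3-4 and 3-6 show urine. No coverage percentage is claimed.

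No effect on the trial's results is claimed. Confidence is medium, because the laboratory manual and the earlier protocols are not available.

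**What to change.** Add a urine pregnancy test for women of childbearing potential at Cohort 1 Screening/Day 0, to be read at the site as negative before the infusion. Make the change in Tables 3-1 and 3-3 and in 6.1.1 and 6.2.1. Keep the serum sample. If the urine test is positive, hold the infusion until the serum result and follow 8.7.

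The cost is one quick test per woman of childbearing potential, on urine already collected at that visit for urinalysis. The downside is an occasional false positive that delays an infusion until the serum result is back.

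If the sponsor extends the result rule to Cohort 2, the cost is higher. Under 4.4.2 a dose outside the visit window counts as missed, a maintenance dose 3 to 7 days late triggers a 2,000 mg reload, and more than two missed doses leads to withdrawal. The extension should therefore also state that a hold for a pending pregnancy result does not count toward withdrawal for missed doses.
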